### **Safety endpoints**

The key safety endpoints for this trial are potentially associated adverse events with the amoxicillin challenge, these are prespecified as:

- Anaphylaxis
- Other potentially allergic symptoms during/after amoxicillin challenge- e.g. rash
- Nausea/Vomiting/GI symptoms only
- Other symptoms during amoxicillin challenge

For reactions to penicillin given during the hospital stay, the same events will be captured:

- Anaphylaxis
- Other potentially allergic symptoms during/after penicillin administration- e.g. rash
- Nausea/Vomiting/GI symptoms only
- Other symptoms during penicillin administration

Due to the nature and clinical course of patients receiving routine hospital care, a substantial number of adverse events are expected among participants, including but not limited to:

- Death
- Sepsis
- Renal failure

- Respiratory failure
- Heart failure
- Pneumonia or other / new infection
- DVT or PE
- Complications related to ICU procedures
- Arrhythmia
- Delirium
- Bowel ischemia
- Ileus
- Leukopenia or leukocytosis
- Anemia or thrombocytopenia
- Coagulopathy (DIC)
- Hypoglycemia
- Electrolyte abnormalities

These adverse events are common in hospitalized patients and are thus not expected to reflect safety of the treatment regimen. There is no plan to summarize or report these events.

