#### Adverse Events

1) Exclusion criteria include patients who are currently medically unstable and unable to receive study procedures, or patients whose primary care is received outside of Vanderbilt University Medical Center. We know that by restricting inclusion to patients who receive the majority of their care at Vanderbilt that this will enable better long term monitoring of adverse events via the EHR.

2) All adverse events will be discussed with and evaluated by a physician investigator as soon as the subject or study personnel report them.

3) Adverse events including SAEs upon initial amoxicillin challenge or upon subsequent administration of penicillin class drugs in patients whose penicillin allergy label has been removed, or any unanticipated problems will be appropriately reported to the IRB, safety monitor, and NIAID. In addition to the IRB review of adverse events outlined above, the PIs will meet at least quarterly with staff to discuss any problems that arise that could compromise patient safety. Meetings will be held more frequently to quickly rectify problems if they arise. When necessary, the IRB will be consulted for further guidance. This is particularly true for reactions, which, in their most severe forms, threaten life or function. A serious AE (SAE) or serious adverse drug experience (SADE) is any untoward medical occurrence that:

- Results in death
- Is life-threatening. "Life-threatening" refers to an event in which the subject is at risk of death at the time of the event; it does not refer to an event which hypothetically might have caused death if it were more severe (ICH E6).
- Requires inpatient hospitalization or prolongation of existing hospitalization
- Results in persistent or significant disability/ incapacity (as per reporter's opinion)
- Is a congenital anomaly/birth defect

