- Is another medically important condition. Important medical conditions that may not result in death, be life-threatening or require hospitalization may be considered as SAEs or SADEs when, based upon appropriate medical judgment, they may jeopardize the subject or may require intervention to prevent one of the outcomes listed in the definition above. Examples of such events relevant to this trial are urticaria, angioedema, respiratory distress, prolonged nausea or vomiting after direct provocation testing with amoxicillin that might be the prelude to anaphylactic shock. [Code of Federal Regulations Title 21, Volume 5, 21CFR312.32, revised April 1, 2006].

4) The PI, staff, and the research coordinators (or qualified persons providing coverage) will be available 24 hours each day to participants and other investigators, should an emergency arise.

5) The Vanderbilt Coordinating Center will submit an annual safety and adverse event report to the NIAID program official and the Vanderbilt IRB.

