### Key secondary endpoints

The secondary endpoints for this trial include the following:

1. Tolerance of an amoxicillin oral challenge, which will be documented using a smart phrase to indicate tolerance or intolerance. This outcome is a binary variable, either yes= tolerated, or no =not tolerated, with relevant symptoms to be determined by chart review.
2. Uptake of the risk stratification tool: This is determined by whether patients with a penicillin allergy label in their chart receive a risk assessment. This is a binary variable, either the patient did or did not receive a risk assessment of their penicillin allergy.
3. Amoxicillin adverse events: In patients who did not tolerate their amoxicillin oral challenge, we will assess the types of adverse events that were reported.
  - a. An immediate allergic amoxicillin challenge adverse event will be defined as an adverse event reported in association with the amoxicillin challenge that includes symptoms of anaphylaxis or rash, with onset within 6 hours of the challenge dose being given.
  - b. A non-immediate allergic amoxicillin challenge adverse event will be defined as an adverse event such as rash that is potentially consistent with allergy, occurring within 24 hours of the dose being given.
  - c. A non-allergic amoxicillin challenge adverse event will be defined as an adverse event, such as gastrointestinal upset, reported in association with amoxicillin challenge, within 6 hours of the challenge dose being given.
4. Communication about penicillin allergy label removal in the discharge summary: This is determined by the presence of language about the penicillin allergy evaluation, challenge, and removal, in those patients who underwent penicillin allergy challenge. The outcome is a binary variable, as this information is either present, or absent.
  - a. This data will be obtained by manual chart review.
  - b. A smart phrase has previously been created that was encouraged to be used for this purpose, and its utilization will be extracted.
5. Longer term penicillin allergy label removal, over 3 months and 18 months of follow up. Among those who underwent a penicillin allergy label removal, whether the allergy remains out of the chart or is “ever/never” re-entered into the chart. The outcome is a binary variable at either 3 months or at 18 months.

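### The SAP's list of unreported events includes death and respiratory failure, has no exception for onset after a challenge or penicillin dose, and there is no SAE summary to catch what falls through

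*SAP*

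**What the plan says.** SAP section 3, Safety endpoints, first names what will be reported: "The key safety endpoints for this trial are potentially associated adverse events with the amoxicillin challenge, these are prespecified as" anaphylaxis, other potentially allergic symptoms, gastrointestinal symptoms only, and a catch-all row, "Other symptoms during amoxicillin challenge". The same four rows are set for penicillin given during the hospital stay.

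It then turns to routine care, where "a substantial number of adverse events are expected among participants, including but not limited to" 17 entries, including death, respiratory failure, renal failure and arrhythmia. The reason given is "These adverse events are common in hospitalized patients and are thus not expected to reflect safety of the treatment regimen", and the conclusion is "There is no plan to summarize or report these events".

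Protocol section 6.0, Adverse Events, item 3, sends to the IRB, the safety monitor and NIAID "Adverse events including SAEs upon initial amoxicillin challenge or upon subsequent administration of penicillin class drugs" in patients whose label has been removed. Its SAE criteria begin with death and life-threatening events. For medically important events it adds: "Examples of such events relevant to this trial are urticaria, angioedema, respiratory distress, prolonged nausea or vomiting after direct provocation testing with amoxicillin".

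The SAP does not use SAE as a category. Its Reporting of Safety Events list has two lines: adverse events associated with the challenge, per total challenges, and adverse events associated with penicillin use in the same hospitalization, per total labelled patients.

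**The concern.** Protocol section 2.0 makes the safety of single-dose oral challenge part of the trial's aim, and the SAP's Safety Analysis section undertakes to report on it. The published challenge risk therefore needs a rule that decides which events after a dose are counted. The SAP gives no rule for a listed event that follows a dose. Whether it belongs to the challenge rows or to the unreported list depends on whether someone linked it to the dose. The SAP's Blinding section confirms that there is no blinding, so that link is made by people who know that the patient was challenged.

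The events most open to this are serious and few. In a series of challenges of modest size, one of them changes the headline safety figure.

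**Working it through.** **Step 1. Where would an event after a challenge be counted?** The classes in SAP section 3, Key secondary endpoints, item 3, and the rows in Safety endpoints, give the following.

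| Event after a challenge dose | Place in the SAP |
|---|---|
| Recognised anaphylaxis within 6 hours | Item 3a and the anaphylaxis row. Counted. |
| Potentially allergic event up to 24 hours | Item 3b and the potentially allergic row, which covers during and after. Counted. |
| Respiratory failure at 3 hours, reported in association with the challenge, charted as not tolerated | Item 3c can take it: "A non-allergic amoxicillin challenge adverse event will be defined as an adverse event, such as gastrointestinal upset" is open wording with a 6-hour window. Counted. |
| The same event, charted as tolerated | Item 3 types events only in patients who did not tolerate the challenge, and the catch-all row is limited to symptoms during it. Only the general line in Reporting of Safety Events could take it, if someone associates it with the challenge. |
| The same event, not attributed to the dose | Item 3c and the general line both need an association. It falls on the unreported list. |
| Serious non-allergic event starting at 6 to 24 hours | Item 3b is for allergic-type events and item 3c stops at 6 hours. No defined class. |

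The first three cases are covered; the last three are not reliably covered. Tolerance is documented by a smart phrase. The order set in protocol section 5.0 takes vital signs at baseline and then twice at 30-minute intervals. Nothing in the documents says that a tolerant entry is reopened if the patient deteriorates later.

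For in-hospital penicillin, the catch-all row is likewise limited to symptoms during administration, and no onset window is given.

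**Step 2. What would one omitted event do?** The plan states no challenge-risk figure, so there is none to reproduce. The following is an illustration only.

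- Intervention unit-months, assuming one of the 12 units crosses over each month from month 1 of 12: 1 + 2 + ... + 12 = 78.
- Labelled patients per unit-month (SAP section 8, Power and Sample Size): 10 to 15. This gives 78 x 10 = 780 to 78 x 15 = 1170.
- Assumed share challenged: 10% to 20%. The SAP gives no challenge rate. These values borrow the size of its pessimistic label-removal proportion and of its target difference.
- Challenges: 780 x 0.10 = 78 to 1170 x 0.20 = 234.

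Exact (Clopper-Pearson) 95% upper limits: with 0 events, 1 - 0.025^(1/n); with 1 event, the 97.5th percentile of Beta(2, n - 1).

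| Challenges | Rate, event counted | Upper limit, event counted | Rate, event omitted | Upper limit, event omitted |
|---|---|---|---|---|
| 78 | 1/78 = 1.3% | 6.9% | 0 | 4.6% |
| 234 | 1/234 = 0.4% | 2.4% | 0 | 1.6% |

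This shows the consequence of one omission. It does not show that an omission would occur.

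**The case against.** The strongest reply is that the list describes background illness and the SAP governs analysis, while the protocol governs reporting to the IRB, the safety monitor and NIAID and adds an annual safety report. Nothing in the SAP cancels those duties and both documents can be followed. That stands. A reader might infer that the SAP directly contradicts the protocol's SAE rules, but the documents show only that the two are not reconciled.

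The reply continues that the SAP already counts much of what matters. Items 3a to 3c reach 6 or 24 hours, the general line is not limited to named types, symptoms are determined by chart review, and the Main Analysis section counts hypotension in failed challenges. This also stands, and it rules out the inference that any respiratory failure a few hours after a challenge goes unreported. It does not reach the last three cases in the table.

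A reader might also infer that vomiting is hidden. It is not: it has its own row. The protocol leaves its classification as serious to medical judgement and does not make all prolonged vomiting an SAE.

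Finally, many listed events, such as anemia or electrolyte abnormalities, are common on medical wards, and the SAP is not designed to compare safety between arms inferentially. It is therefore reasonable not to tabulate every non-serious listed event. Deaths by arm would also be hard to read, because arm is tied to unit and calendar time in a stepped wedge.

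**Conclusion.** The point holds as a gap in the safety summary. The exclusion is open-ended, includes death and respiratory failure, has no exception for onset after a dose, and is not backed by an SAE table. Three kinds of serious event can drop out of the reported challenge risk: those in patients charted as tolerant, those not attributed to the dose, and non-allergic ones starting at 6 to 24 hours. The risk could then be understated; the documents do not show that it will be.

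Under the assumptions of 78 intervention unit-months, 10 to 15 labelled patients in each and 10% to 20% challenged, one omitted event takes the observed rate from between 1.3% and 0.4% down to zero and lowers the upper limit by about a third (6.9% to 4.6%, or 2.4% to 1.6%). It is tempting to set these rates against the under-1% figure in the protocol's alert text, but that figure is the chance of a positive skin test and is not comparable with a challenge-reaction rate.

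This should be corrected. It does not affect the primary endpoint.

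**What to change.** 1. Limit the non-reporting sentence in SAP section 3 to events that neither meet the protocol's SAE criteria with onset within 24 hours of the challenge dose nor are reported in association with a challenge or penicillin dose. The SAP already uses 24 hours in item 3b.
2. Add an SAE row for the challenge to Reporting of Safety Events. It should count events with onset within 24 hours of the dose, whatever cause was given and whether or not the challenge was charted as tolerated, with the attributed cause in a footnote.
3. Add an SAE row for in-hospital penicillin treatment, and state which events it counts, since the SAP sets no onset window there.
4. Reconcile the SAP with protocol section 6.0, including that the protocol covers later penicillin after label removal while the SAP's safety endpoints stop at the hospital stay.

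The cost is a few sentences, two table rows and a date-limited query of the health record. The downside is that some background serious events will appear in the table. The documents give no rate for these, but the restriction to serious events within 24 hours should keep them few, and the footnote lets a reader judge them.

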## 8. DESIGN CONSIDERATIONS

### Randomization

During the trial, randomization will occur at the level of the medical unit. A single medical unit will serve as a cluster. Twelve medical units were selected for inclusion, and the order of starting the intervention was randomized, staggered by one-month intervals.

### Adaptations and stopping

No adaptations are anticipated, and no stopping rules are implemented.

### Power and Sample Size

To power this study, we assumed 0.5% of patients would have their penicillin allergy label intentionally removed or would receive a test dose challenge in the control condition, based on our observation of usual care for a six-month period at the participating units. Preliminary data further suggest that around 100 patients per month are admitted and discharged from each participating medical unit, and that 10-15% of all patients admitted have a penicillin allergy listed in their chart. Hence, approximately 10-15 penicillin allergic patients would be eligible for inclusion in the intervention group, per unit, per month.

Our sample size was selected to detect a clinically meaningful difference of 20 additional penicillin-allergic patients per 100 having their penicillin allergy label removed using our intervention. Assuming pessimistically that a minimum of 10% of patients randomized to intervention will undergo risk stratification leading to an allergy label removed, and that 0.5% of patients in the control group will have a penicillin allergy label removed during current practice, 1:1 allocation of participants, an alpha of 0.05, power of 0.8 and a two-sided test of differences in proportions, we would need a minimum of 35 patients per group (70 total) to detect a minimally clinically meaningful 20% increase in penicillin allergy label removals. Much smaller sample sizes will be needed to see effects if higher engagement

and utilization is observed. By running this study with one year of intervention (12 medical units with one month step lengths), we will greatly exceed the sample size needed for the main analysis, and we will have sufficient data to report on the secondary outcomes with precision.

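### The 35 per group in the sample-size paragraph fits a 20-point difference, not the 10% removal rate printed as its input; 10% needs 76 or 86 per group (minor consequence)

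*SAP*

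**What the plan says.** The SAP, section 8, Power and Sample Size, first sets the target: "Our sample size was selected to detect a clinically meaningful difference of 20 additional penicillin-allergic patients per 100". It then lists the inputs of the calculation. With intervention, "a minimum of 10% of patients randomized to intervention will undergo risk stratification leading to an allergy label removed". In control, "0.5% of patients in the control group will have a penicillin allergy label removed during current practice". Allocation is 1:1, alpha 0.05, power 0.8, with a two-sided test of proportions. The result is that "we would need a minimum of 35 patients per group (70 total) to detect a minimally clinically meaningful 20% increase". The next sentence adds: "Much smaller sample sizes will be needed to see effects if higher engagement" and utilization are seen.

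Protocol 8.0 is built the same way and also arrives at 35 per group, but its calculation uses a control removal rate of 0.1%, after giving 0.5% earlier in the section. Both documents introduce the 0.5% as a composite; in the SAP, "we assumed 0.5% of patients would have their penicillin allergy label intentionally removed or would receive a test dose challenge in the control condition". The Protocol's calculation also ends on removals or amoxicillin challenges. The primary endpoint in SAP section 3 is label removal alone.

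On actual size, the SAP expects that "approximately 10-15 penicillin allergic patients would be eligible for inclusion in the intervention group, per unit, per month", across 12 units with one-month steps, and says that "we will greatly exceed the sample size needed for the main analysis". The Protocol calls the study intentionally overpowered for label removal.

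**The concern.** One sentence carries two incompatible effect sizes. A 10% rate cannot be a 20-point increase over 0.1% or 0.5%. The 10% stands in the list of inputs, and the following sentence says that higher engagement would need far fewer patients. A reader will therefore take 35 as the requirement in the low-engagement case and conclude that 70 patients give 80% power at 10% removal. That is false, and a trial report that copies the paragraph would repeat it. What is at stake is the accuracy of the stated calculation, not whether the trial is large enough.

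**Working it through.** **Inputs.** From SAP section 8 and Protocol 8.0: two-sided alpha 0.05 (z = 1.960), power 0.80 (z = 0.8416), 1:1 allocation. Intervention rate p1 = 10%, or control plus 20 points. Control rate p0 = 0.5% (SAP) or 0.1% (Protocol calculation). The documents name no formula, so the pooled normal approximation is used first and others follow as a check.

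**Formula**, per group, with d = p1 − p0 and p̄ = (p0 + p1)/2:

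n = [1.960·√(2p̄(1−p̄)) + 0.8416·√(p0(1−p0) + p1(1−p1))]² / d²

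**Reproducing the plan's 35 (20-point difference).**
- 20.1% vs 0.1%: (0.8352 + 0.3383)² / 0.200² = 34.43, so 35. This is the printed figure.
- 20.5% vs 0.5%: (0.8497 + 0.3449)² / 0.200² = 35.68, so 36.

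**The printed 10% rate.**
- 10% vs 0.5% (SAP): (0.6182 + 0.2594)² / 0.095² = 85.33, so 86 (172 total).
- 10% vs 0.1% (Protocol): (0.6070 + 0.2539)² / 0.099² = 75.61, so 76 (152 total).

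**Other methods**, per group, two-sided:

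| Comparison | Pooled | Unpooled | Continuity-corrected | Arcsine |
|---|---|---|---|---|
| 10% vs 0.5% | 86 | 83 | 106 | 63 |
| 10% vs 0.1% | 76 | 73 | 95 | 47 |
| 20.5% vs 0.5% | 36 | 33 | 46 | 25 |
| 20.1% vs 0.1% | 35 | 32 | 44 | 21 |

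Exact Fisher calculations at 10% give about 91 (control 0.5%) and 80 (control 0.1%). No two-sided method gives 35 at 10%. A one-sided arcsine calculation for 10% vs 0.1% gives 37, but both documents state a two-sided test. Reading the 20% as relative fails too: 10% vs 12% needs 3,841 per group and 0.5% vs 0.6% needs 85,862. Reading it as 10% vs 30% gives 62.

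**Power of 35 per group**, Φ{[d·√35 − 1.960·√(2p̄(1−p̄))] / √(p0(1−p0) + p1(1−p1))}:
- 10% vs 0.5%: 0.428 (exact power of the chi-square test 0.413).
- 10% vs 0.1%: 0.472 (exact 0.457).
- 20.5% vs 0.5%: 0.792. 20.1% vs 0.1%: 0.807.

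These describe a trial of 70 patients, not this trial.

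**Does the trial's size hold up?** The total is not stated, but it follows from the documents: 12 units × 12 months × 10–15 = 1,440–2,160 labeled patients. Suppose one unit is live from month 1 and one is added each month. Then there are 78 intervention and 66 control unit-months, or 780–1,170 and 660–990 patients. Even the smallest group is 660/86 = 7.7 times the larger corrected minimum.

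Clustering needs an intracluster correlation (ICC), which the documents do not give; values up to 0.10 are assumed here. The Hussey–Hughes variance for I units, T periods and m patients per unit-month is

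I·σ²(σ² + Tτ²) / [(IU − W)σ² + (U² + ITU − TW − IV)τ²]

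with σ² = (1 − ICC)p̄(1−p̄)/m and τ² = ICC·p̄(1−p̄). U is the number of intervention unit-months. W and V are the sums of squared period totals and squared unit totals. At I = T = 12, U = 78, W = V = 650, m = 10, ICC = 0.10 and 10% vs 0.5%: σ² = 0.00448, τ² = 0.00497, variance = 0.000351, SE = 0.0187. Power is Φ(0.095/0.0187 − 1.960), about 0.999, the lowest value over the range examined.

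This is a linear approximation, and control events are few: 66 unit-months × 10–15 × 0.5% gives 3.3–5.0 expected removals. A simulation closer to the planned model (logistic, unit random intercept, linear time, no patient covariates, assumed unit SD 0, 0.5 or 1.0 on the logit scale) rejected in 300 of 300 runs in each of six settings (lower 95% bound 98.8%).

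**The case against.** The best defense is that 35 was always meant for the 20-per-100 target. The SAP paragraph opens with that target and the sentence closes on it, and 35 is right for it to within one patient. On that view the 10% clause is a stray remark in a reproducible calculation. That stands in part: the documents do not settle which element is out of place, and the fair description is an internal contradiction. It does not rescue the text. The 10% is printed as an input, it is described as leading to label removal and so cannot mean engagement alone, and the next sentence presents 35 as the low-engagement figure.

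The two control rates are weak evidence of error in themselves. Near a 20-point difference the control rate hardly moves the answer (34.4 vs 35.7). With an intervention rate of exactly 20%, 35 comes out of either control rate if the formula may differ: pooled 34.6 for 0.1%, unpooled 34.05 for 0.5%. This part is a consistency point and a reason to name the formula. The composite wording is likewise a side issue of definition.

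Finally, nothing in the trial depends on 35. Enrollment is fixed by 12 units and 12 months, there is no interim analysis or stopping rule, and both documents say the size will far exceed the minimum. That is correct and is why the consequence is minor. It does not make the printed figure right.

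**Conclusion.** The concern holds. Under the stated test, 35 per group does not follow from a 10% removal rate. The requirement is 86 with the SAP's control rate or 76 with the Protocol's, and 35 would give about 43% or 47% power instead of 80%. The 35 belongs to a 20-point difference. The exact values 76, 86, 35 and 36 rest on the pooled normal formula and individual randomization, but the conclusion does not depend on the choice among the two-sided methods tried. The consequence is minor: on the documents' own admission figures, and over the assumed ICC range, power at 10% vs 0.5% stays very high. That last statement rests on assumed clustering and on models simpler than the planned adjusted one.

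**What to change.** Reconcile the 10% rate with the 20-point target; the authors should choose which they meant.

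- **Option A.** Keep the 20-point difference and state the matching intervention rate and size: 20.1% vs 0.1%, 35 per group (70 total), or 20.5% vs 0.5%, 36 per group (72 total), pooled formula. Remove the 10% clause or give it as a separate scenario with its own n.
- **Option B.** Keep 10%, drop the 20% increase, and state 76 per group (152 total) for a 0.1% control rate or 86 per group (172 total) for 0.5%.

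In either case, name the formula, use one control rate for label removal alone in both documents, and say that the figure is an individually randomized minimum before clustering. A stepped-wedge power figure over a stated ICC range would support the claim of ample size, but is optional. If the SAP is closed, put the correction in a dated note and in the sample-size paragraph of the trial report.

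The cost is a corrected sentence in two documents and a short recalculation. No patients are added, and design, endpoint and analysis stay as they are. The one drawback is that under Option B the stated minimum total rises from 70 to 152 or 172, which looks less favorable.
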